4.4 Schedule of Routine Tests

Tables 8 thru 12 provide the schedule of routine tests, revision 6/10/93. In subsequent chapters the justification for each test is provided.

TABLE 8
Routine Test Schedule
GROUP 1

TEST	TIMING (MONTHS ON STUDY)																												
	0	3	4	6	8	9	12	16	18	20	24	28	30	32	36	40	42	44	48	52	54	56	60	64	66	68	72	76	78
SERUM IG	X						X				X				X				X				X						
CD 3/4/8	X						X				X				X				X				X						
DHST (1)	X						X				X				X				X				X						
CHV CULTURE (2)																													
CHV SEROLOGY (2)																													
EBV CULTURE (2)																													
EBV SEROLOGY (2)																													
CBC	X						X				X				X				X				X						
ESR	X						X				X				X				X				X						
LDH	X						X				X				X				X				X						
SERUM STORAGE	X						X				X				X				X				X						
PULMONARY EXAM	X	X					X				X				X				X				X						
SP02	X	X					X				X				X				X				X						
CXR	X						X				X				X				X				X						
PFT	X						X				X				X				X				X						
CARDIAC ASSESS.	X						X				X				X				X				X						
EKG	X						X				X				X				X				X						
HOLTER	X						X				X				X				X				X						
ECHO	X						X				X				X				X				X						

(1) Children one year or older

(2) These tests are done only when clinically warranted

TABLE 9
 Routine Test Schedule
 GROUP II (Months 0 - 6)

TEST	TIMING FROM BIRTH (MONTHS)				
	0	3	4	6	
ELISA					
W. BLOT					
HIV CULTURE	X	X			X
SERUM IG	X				X
CD 3/4/8	X	X			
DHST					
CMV CULTURE (1)	X				X
CMV SEROLOGY (1)					X
EBV CULTURE	X				X
EBV SEROLOGY					X
CBC	X				X
ESR					X
LDH	X				X
SERUM STORAGE	X				X
PULMONARY EXAM	X	X			X
SPO2	X	X			X
CXR		X			
PFT					X
CARDIAC ASSESS.	X				X
EKG	X				
HOLTER	X				
ECHO	X				X

(1) CMV serology testing discontinued when child is positive for CMV infection.
 CMV culture continues to be taken and stored.

TABLE 10
Routine Test Schedule
GROUP 11a (MONTHS 8-78)

TEST	TIMING FROM BIRTH (MONTHS)																											
	8	9	12	15	16	18	20	21	24	28	30	32	36	40	42	44	48	52	54	56	60	64	66	68	72	76	78	
HIV CULTURE																												
SERUM IG			X			X			X				X					X						X				
CD 3/4/8				X				X					X					X						X				
DHST			X						X				X					X						X				
CMV CULTURE(1)			X			X			X				X					X						X				
CMV SEROLOGY(1)			X			X			X				X					X						X				
EBV CULTURE			X			X			X				X					X						X				
EBV SEROLOGY			X			X			X				X					X						X				
CBC			X			X			X				X					X						X				
ESR			X			X			X				X					X						X				
LDH			X			X			X				X					X						X				
SERUM STORAGE			X			X			X				X					X						X				
PULMONARY EXAM			X			X			X				X					X						X				
SPO2			X			X			X				X					X						X				
CXR			X			X			X				X					X						X				
PFT			X			X			X				X					X						X				
CARDIAC ASSESS.	X		X			X			X				X					X						X				
EKG			X			X			X				X					X						X				
HOLTER			X			X			X				X					X						X				
ECHO	X		X			X			X				X					X						X				

(1) CMV serology testing discontinued when child is positive for CMV infection.
CMV culture continues to be taken and stored.

TABLE 11A

Routine Test Schedule

GROUP 11b - CONTROLS (MONTHS 8-78)

TEST	TIMING FROM BIRTH (MONTHS)																												
	8	9	12	15	16	18	20	21	24	28	30	32	36	40	42	44	48	52	54	56	60	64	66	68	72	76	78		
ELISA						X																							
M. BLOT						X ¹																							
HIV CULTURE																													
SERUM IG			X			X		X		X		X		X		X		X		X		X		X		X		X	
CD 3/4/B			X		X		X		X		X		X		X		X		X		X		X		X		X		X
DHST																													
CMV CULTURE (2)			X			X		X		X		X		X		X		X		X		X		X		X		X	
CMV SEROLOGY (2)			X			X		X		X		X		X		X		X		X		X		X		X		X	
EBV CULTURE			X			X		X		X		X		X		X		X		X		X		X		X		X	
EBV SEROLOGY			X			X		X		X		X		X		X		X		X		X		X		X		X	
CBC			X			X		X		X		X		X		X		X		X		X		X		X		X	
ESR			X			X		X		X		X		X		X		X		X		X		X		X		X	
LDH			X			X		X		X		X		X		X		X		X		X		X		X		X	
SERUM STORAGE			X			X		X		X		X		X		X		X		X		X		X		X		X	
PULMONARY EXAM			X			X		X		X		X		X		X		X		X		X		X		X		X	
SPO2			X			X		X		X		X		X		X		X		X		X		X		X		X	
CXR			X			X		X		X		X		X		X		X		X		X		X		X		X	
PFT			X			X		X		X		X		X		X		X		X		X		X		X		X	
CARDIAC ASSESS.			X			X		X		X		X		X		X		X		X		X		X		X		X	
EKG			X			X		X		X		X		X		X		X		X		X		X		X		X	
HOLTER			X			X		X		X		X		X		X		X		X		X		X		X		X	
ECHO			X			X		X		X		X		X		X		X		X		X		X		X		X	

(1) As required by Protocol

(2) CMV serology testing discontinued when child is positive for CMV infection. CMV culture continues to be taken and stored.

TABLE 11B

Routine Test Schedule

GROUP 11b - NON-CONTROLS (MONTHS 8-78)

TEST	TIMING FROM BIRTH(MONTHS)						
	8	9	12	15	16	18	
ELISA							x
W. BLOT							x ¹

(1) As required by Protocol

TABLE 12
Routine Test Schedule
GROUP 11b MOTHERS

TEST	WITHIN ONE MONTH OF EDC
IMMUNOLOGIC STUDIES	X
CMV CULTURE	X
CMV SEROLOGY	X
EBV CULTURE	X
EBV SEROLOGY	X

Blank page

Blank page

5. Methods

5.1 Clinical and Laboratory Evaluation of Subject

Laboratory evaluation of subjects will be coordinated with other protocols at each institution to avoid duplication of studies, to minimize discomfort, and to decrease costs.

5.1.1 Initial Visit and Assessment of Mothers

Each of the five Clinical Centers is staffed by obstetrical departments which serve the health care facilities for indigent women. Through direct participation with the clinical centers, the obstetrical departments are already screening high-risk pregnant women for HIV-infection. High-risk mothers include those who are intravenous drug abusers and those with sexually transmitted diseases. A woman is considered to be at high risk for HIV infection if she admits to drug abuse, shows physical evidence of drug abuse, or has urine which tests positive for illicit drugs. Other factors that would place a woman into an HIV high risk group include: sexual relations with a person with HIV infection or with an intravenous drug abuser, country of origin of high prevalence rate of HIV infection, or multiple sexual partners. A woman is considered to have a sexually transmitted disease by her own admission or by testing of blood for typical infectious agents including hepatitis B.

It is estimated that 2 to 5% of all pregnant women delivering at indigent care facilities fall into the high-risk category. The collaborating obstetrical co-investigator(s) will inform the principal investigator(s) of the pending or recent delivery of a baby born to an HIV-positive mother, using the established paramedical system, (e.g., research nurse, data manager, social worker). A pediatric co-investigator or representative will visit the mother near the time of delivery to discuss enrollment of the child in this study.

For Group II, the initial visit of the mother-to-be or mother and infant will take place prepartum in the obstetrical clinic or postpartum in the hospital or pediatric clinic (up to 28 days after birth). If the mother has already been proved to be HIV-positive, documentation will be obtained and no further diagnostic tests to establish that fact need be done. Otherwise, blood specimens will be obtained for HIV antibodies, and/or HIV culture and/or special diagnostic tests (See Section 5.1.2). If the woman presents prepartum, the obstetrician will evaluate the pregnant woman for historical facts suggestive of HIV-infection and perform a physical examination to determine whether there are findings of primary HIV-infection (lymphadenopathy, hepatosplenomegaly, wasting) or opportunistic infection (oral candidiasis, pneumonitis, encephalopathy). If the woman is evaluated postpartum, the pediatrician will rely upon the woman's medical history and medical records for an evaluation of her HIV-status. The HIV-status will be defined postpartum by laboratory tests in the same manner as prepartum.

5.1.2 HIV Testing of Mother and Infants

The conventional tests for HIV antibody (ELISA and Western Blot) will be used to establish a diagnosis of HIV infection in pregnant women. If these tests yield indeterminate values other diagnostic tests will be employed (e.g., HIV culture). HIV cultures will be performed on Group II children at month 00 (not cord blood), 03 and 06. Two positive cultures will be necessary to assign a patient to Group IIa (infected). Two negative cultures, one of which must be the month 06 culture, will be necessary to assign a patient to Group IIb (noninfected). It is expected that approximately 20% of infants will be identified as Group IIa.

ELISA will be performed on all Group IIb patients (control and non-control) at month 18 to confirm their HIV-negative status. A positive ELISA result will require performance of Western Blot for confirmation of HIV status.

5.1.3 Immunologic/Virologic Assessment of Infants in Group I

Infants in Group I will be those documented with vertical transmission of HIV-infection who are over 28 days of age. Approximately 200 infants and children total will be enrolled at the five centers. The time sequence of visits and immunologic/virologic tests are contained in Table 8. Although patients will be seen in clinic for other components of this study, the immunologic/virologic testing of Group I will be less intense and, in general, tests will be performed on an annual basis. The types of tests selected for Group I patients are those which will permit correlation of cardiac and pulmonary condition with HIV disease state as reflected in the degree of immunodeficiency and the extent of coinfection with CMV and EBV. Western Blot banding patterns have been associated with stages of HIV infection. For example, the loss of antibody to p24 Ag on Western Blots has been associated with advanced HIV disease (Falloon et al, 1989). Serum immunoglobulin (Ig's) are known to be a very sensitive index of HIV-infection in infants and children, frequently rising well beyond the normal ranges in early disease and falling in terminal disease (Falloon et al, 1989). Leukocyte markers (CD3, CD4, and CD8 cell counts) are perhaps the most sensitive in vitro assessment of the stage of HIV-infection, with CD4 cell counts of less than 200 indicative of a precarious state of health (Falloon et al, 1989). Delayed hypersensitivity skin tests (DHST) are a reliable means of testing specific T-cell recall of antigens, and can be used to determine anergy. Testing will be performed on children over 1 year of age. Cultures and serologic tests for CMV and EBV can be utilized in conjunction with tests of cardiac and lung function to determine the role these viruses play in accelerating the complications of HIV-infection. For Group I patients, these tests will be obtained when the patients are symptomatic, according to the schedule outlined in Table 8. Listed in Table 8 are clinically warranted tests (CBC, LDH, ESR, stored serum) which will be obtained on a 12 month schedule, except when intercurrent or chronic disease occurs. When patients develop intercurrent or chronic illness, these tests will be repeated (six times per year estimate); in addition, serum Ig's, lymphocyte subsets (CD3, CD4, CD8), DHST's-70°C serum (storage) will be repeated unless performed within 2 month's; CMV and EBV cultures will be obtained for chronic illness if previous cultures were negative. In addition, viral cultures for influenza, parainfluenza, RSV, and adenovirus

5.1.4 Immunologic/Virologic Assessment of Mothers and Infants in Group II

Infants in Group II (and their mothers) will be recruited into this prospective study on the basis of positive HIV ELISA and Western Blot tests. At least 80% of the HIV-positive mothers will be recruited prepartum to permit fetal echocardiography measurements to be made upon the fetus. Since the health of HIV-infected mothers may influence HIV transmission to their fetuses and thus predispose their living infants to lung and heart disease, several important immunologic and virologic tests will be performed on the mothers (Table 12). All of the mothers will have been previously tested for the presence of HIV by means of the ELISA and Western Blot tests. Mothers will be tested for CMV and EBV infection prepartum or at the time of delivery. Urine, will be cultured for CMV and throat washings (saliva) will be cultured for EBV. In addition, serologic tests for CMV and EBV will be obtained. The purpose of the virologic tests is not only to determine possible virologic cofactors in mothers but, more importantly to determine which infants are likely to acquire CMV and EBV by vertical transmission; to date vertical transmission of EBV has not been established. Infants receiving double, or triple, virus infection from their mothers are expected to display more severe and complex HIV disease, including cardiovascular and pulmonary complications (Falloon et al, 1989). For example, HIV-infected infants who develop LIP/PLH may have been congenitally infected with EBV as well as HIV. The state of maternal immunodeficiency secondary to HIV-infection may also play a crucial role in causing severe heart and lung complications of HIV-infection in developing infants. Thus, CD3, CD4, and CD8 cell counts will be assessed in mothers either before or near the time of delivery.

Table 9 displays the schedule of tests for immunologic function and viral infection for Group II patients from birth through 6 months. Twenty percent of these at risk infants are expected to be infected and identified by 6 months of age. The remaining 80% of the Group II patients are expected to lose seropositivity and be identified as Group IIb, thus forming a control cohort. Test schedules for Group IIa and IIb from months 8-78 are shown in Tables 10 and 11, respectively.

Group II infants will be cultured for CMV (urine) infection and EBV (throat washings/saliva) at 6 month intervals. Infants testing positive for CMV at birth or up to 28 days after delivery will be assumed to have acquired the infection on a congenital basis. After infants have become CMV positive (positive culture at any age or positive serology in children \geq 12 months of age), urine will continue to be collected but will be stored at -70° (freezer) for subsequent culture analysis. CMV serology, however, will be discontinued. Urine specimens are to be frozen in antibiotic solution and 50% glycerine in vials as described

in Section 5.3.7.1.2 in the Manual of Operations. At an appropriate time in the future, these frozen urine specimens will be sent to a central laboratory ([name]) for CMV culture. Both EBV cultures and serologies will be continued after the child becomes EBV-positive.

The immunocompetence of the infants in Group II will be assessed on a prospective basis by measuring serum immunoglobulin levels, and leukocyte subsets (CD3, and CD4/CD8) and DHST. As discussed above, these selected tests of immunologic function convey information not only of the state of immunologic health of the infant but also are a measure of the extent of HIV disease in infected infants. Also listed in Table 9, 10 and 11 are four clinically indicated tests (CBC, ESR, LDH, and stored serum) which will be obtained on a 6 month schedule, except when intercurrent or chronic disease occur. When patients develop intercurrent or chronic illness, these tests will be repeated (six times per year estimate); in addition serum Ig's, lymphocyte subsets (CD3, CD4, CD8), DHST's, -70°C serum (storage) will be repeated unless performed within 2 months; CMV and EBV cultures will be obtained for chronic illness if previous cultures were negative. In addition, viral cultures for influenza, parainfluenza, RSV, and adenovirus will be obtained.

5.1.5 Diagnostic Evaluation of Symptoms not Associated with Pulmonary or Cardiovascular Complications

From time to time, infants infected with HIV will develop symptoms due to complications in organ systems other than the lung and heart. They may, for example, develop loss of motor milestones, develop frank encephalopathy, intractable diarrhea with malnutrition, or renal disease. These complications of HIV infection will be recorded in the medical histories of the children that will be obtained at 3 month clinic visits. Primary care physicians or other specialists will care for patients with these complications.

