3.2.6 Bacterial Infections

Bacterial pneumonia occurs more frequently in children with AIDS than in adults with AIDS (Vernon et al, 1988) and in fact recurrent bacterial infections are one of the diagnostic criteria for AIDS in HIV-positive children (Rogers, 1985). The most common offenders are the encapsulated organisms such as Streptococcus pneumoniae, Haemophilus influenzae b and Staphylococcus aureus. As the immunodeficient state progresses, infection with Gram-negative organisms such as Escherichia coli, Klebsiella, and Pseudomonas aeruginosa may result in a severe necrotizing bronchopneumonia. Institution of an aggressive broad-spectrum antibiotic therapy is recommended when there is clinical suspicion of bacterial disease. In addition, chronic gammaglobulin administration is being considered for treatment of patients suffering repeated bacterial infection.

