4.3 Recruitment and Follow-up

4.3.1 Recruitment Strategies

Recruitment of infants and children for this study will utilize the resources of the following ongoing pediatric AIDS research projects:

1. Pediatric AIDS Clinical Trial Group (ACTG), (NIAID),
2. Randomized Clinical Trial of Intravenous Immunoglobulin vs. Placebo in HIV Infected Symptomatic Children (IVIG), (NICHD), and
3. Women and Infants HIV Transmission Study (WITS), (NIAID and NICHD).

All five participating Clinical Centers have one or more of these NIH-funded ongoing research projects and have access to established patients and referral patterns for enrolling new patients. Moreover, all five Clinical Centers have built-in obstetrical components which will be recruiting high-risk pregnant women in large urban indigent health care facilities. Specific enticements will be used in this study to enhance recruitment and follow-up of patients; these include taxi-cab vouchers, day-care services and meal vouchers. In addition, Centers will dedicate ancillary personnel (nurses, social workers, aides) to this specific research; at least one member of the ancillary staff will be bilingual. It must be acknowledged, that the NIAID and NICHD treatment trials in HIV infected children, will have direct impact on the natural history of the cardiovascular and pulmonary complications of pediatric HIV infection, since most children will be taking some form of antimicrobial agent or antiretroviral agent. With the exception of the intravenous immunoglobulin study, it is unlikely that the newer protocols will contain a placebo arm. Therefore, careful medical histories and protocol enrollments must be recorded.

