To determine whether diagnostic methods are able to detect cardiac or pulmonary disease before signs or symptoms appear in HIV-infected children (Objective O2), the sensitivity, specificity and positive and negative predictive values of each method will be determined. In order to determine the optimal cut-point for a diagnostic measure, a receiver operating characteristic (ROC) analysis will be performed (Metz, 1978). Combinations of diagnostic methods that may better detect disease will be evaluated using logistic regression analysis. The specific diagnostic methods likely to be of value are: LDH or PO_2 (or $A-aO_2$) for PCP, IgG for lymphoproliferative lung disease, echocardiogram measures (e.g., fractional shortening) for ventricular disease EKG measures (e.g., PR interval) for detecting arrhythmia, and DTPA for detecting early lung disease.

To evaluate whether PCP accelerates the rate of lung function decline, (Objective O4), the decline in children with and without PCP can be compared using an unpaired t test or a Wilcoxon rank sum test. More elaborate longitudinal data analyses are described in Section 7.3. To determine whether PCP shortens the life span of HIV-infected children with chronic lung disease (Objective O4), a survival analysis will be performed. Detailed discussion of such an analysis is described in Section 7.4.

All hypotheses and objectives referring to HIV-infected children apply to children in Groups I and IIA.

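### In Group II a positive CMV serology from 12 months counts as infection even if drawn under therapeutic immunoglobulin, which can bias the CMV part of H3

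*Protocol*

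**What the plan says.** Protocol 5.1.4 gives two routes to the CMV-positive label in Group II: a "positive culture at any age or positive serology in children" of at least 12 months. Once the label is given, "CMV serology, however, will be discontinued", while "urine will continue to be collected but will be stored at" freezer temperature, for central culture at an unspecified later time. The footnotes to Tables 9, 10 and 11A repeat the stopping rule. For EBV the same section does the opposite: "Both EBV cultures and serologies will be continued after the child becomes EBV-positive".

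Immunoglobulin treatment is in view elsewhere. Section 4.3.1 names three parallel projects as recruitment resources, one of them a "Randomized Clinical Trial of Intravenous Immunoglobulin vs. Placebo in HIV Infected Symptomatic Children". The Introduction expects subjects to take part in other treatment studies and requires treatments to be recorded on the forms. Section 3.2.6 says that "chronic gammaglobulin administration is being considered for treatment of patients suffering repeated bacterial infection".

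H3 (2.3) relates cardiovascular disease in HIV-infected children to EBV and CMV infection. H4 relates lymphoproliferative lung disease to EBV only. Section 7.2 analyses both by stratified Mantel-Haenszel tests or logistic regression in Groups I and IIa, and does not name immunoglobulin among the factors. Section 2 says the secondary hypotheses matter as much scientifically as the primary ones.

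**The concern.** The protocol knows that passive antibody misleads. It waits for maternal antibody to disappear before confirming HIV-negative status (4.2), and it sets a 12-month floor on CMV serology. That floor does nothing about antibody given as treatment at 14 or 20 months. A site following 5.1.4 to the letter would label an uninfected recipient with a positive serology as CMV positive and order no further serology. No sentence says that a later negative culture reverses the label.

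This matters if exposure tracks the outcome. The parallel trial admits symptomatic children, and the indication in 3.2.6 is repeated bacterial infection. Section 5.3.2 reports that abnormal increase in left ventricular mass was more common in symptomatic children. If Group IIa children with cardiac disease receive immunoglobulin more often, false CMV positives concentrate among them, and H3 could show a CMV association with no viral effect behind it.

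**Working it through.** The plan states no figure on this point, so there is none to reproduce. The check asks how large a spurious association the rule could produce when CMV has no effect on cardiac disease.

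**Inputs.** None of the first three is in the protocol; all are assumptions.
- c, true CMV prevalence, equal in diseased and non-diseased children: 20% to 60%.
- i1 and i0, probability of immunoglobulin exposure with and without cardiac disease: 30% or 50% against 10% or 20%.
- s, probability that an exposed, CMV-uninfected child tests seropositive: 0.3 to 1.0.
- Proportion with cardiac disease: 26%, taken as an assumption (Table 5 gives 26% for pericardial effusion at 2.5 years).
- Group sizes from 4.2: about 120 in Group IIa and 200 in Group I, so 320 together. Two-sided alpha 1% from 7.1.

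**Formula.** Labelled positivity is p = c + (1 − c) × i × s, with i = i1 in diseased and i0 in other children. Spurious OR = [p1/(1 − p1)] / [p0/(1 − p0)].

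| Case | c | i1 v i0 | s | p1 | p0 | OR |
|---|---|---|---|---|---|---|
| Lowest unequal | 0.60 | 0.30 v 0.20 | 0.3 | 0.636 | 0.624 | 1.05 |
| Middle | 0.40 | 0.50 v 0.20 | 0.6 | 0.580 | 0.472 | 1.54 |
| Highest | 0.20 | 0.50 v 0.10 | 1.0 | 0.600 | 0.280 | 3.86 |
| Equal exposure | 0.40 | 0.20 v 0.20 | any | equal | equal | 1.00 |

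**False rejection, middle case** (normal approximation, two proportions):
- 120 children, 31 diseased and 89 not: difference 0.108, null SE 0.104, alternative SE 0.103. z = (0.108 − 2.576 × 0.1043)/0.1032 = −1.56, so rejection is about 6% against a nominal 1%.
- 320 children, 83 and 237: null SE 0.0638, alternative SE 0.0631. z = (0.108 − 2.576 × 0.0638)/0.0631 = −0.89, so about 19%.

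Across the unequal cases, rejection runs from about 1% to 73% with 120 children, and from about 1% to over 99% with 320. The 320 figures assume the same labelling in Group I. Since 5.1.4 writes the rule only for Group II, the 120 figures are nearer the mark.

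**After the fix.** Stratify the middle case on exposure. Among exposed children, positivity is 0.40 + 0.60 × 0.6 = 0.76 whether or not they have disease; among unexposed children it is 0.40 in both. The OR within each stratum is 1.00. If serology drawn under exposure is not counted and culture finds infection equally well in all children, p = c in both groups and the OR is again 1.00. If culture misses some infections, exposed children are under-classified, which is why the stratum is needed as well.

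**The case against.** The case against has real force, and parts of it stand.

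- **EBV and H4.** A reader might infer that the same rule distorts H4 and the EBV half of H3. It does not: EBV culture and serology both continue after a positive result. Infused antibody might still affect an individual EBV reading, but not through this rule.
- **Recruitment.** A reader might infer that the cohort is drawn from immunoglobulin-treated children. The trial is one of three named sources, has a placebo arm and enrols symptomatic infected children, which fits Group I. Group II enters by 28 days of age, so Group IIa exposure would come mainly from later treatment. Section 3.2.6 is background and says only that gammaglobulin is under consideration.
- **Permanence.** A reader might call the label irreversible. Urine is kept for culture, serum is stored and treatments are recorded, so it can be re-examined. Repeat serology during continued infusions would not correct a passive positive either; culture would. What remains is that no rule directs the re-examination, and serology after infusions end is lost.
- **Certainty.** Random allocation within the parallel trial does not tie exposure to sickness. The protocol names no CMV assay and does not say how long infused antibody would register. It cannot be said that the rule creates an association, only that it can.
- **Analysis plan.** The choice of covariates may be left to an SAP that is not shown. That is fair for adjustment. It does not cure a case definition written into the protocol that admits passive antibody as infection.

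Section 7.2 also lists "IgG for lymphoproliferative lung disease" among candidate diagnostic measures. Whether infusions disturb that measure is a separate question and does not follow from the CMV rule.

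**Conclusion.** The point holds for CMV in Group II and for the CMV part of H3. The definition in 5.1.4 guards against one source of passive antibody and not against another that the protocol itself foresees, and it stops serology on the result. Bias away from the null requires that sicker Group IIa children receive more immunoglobulin and that exposed uninfected children can test seropositive; the protocol makes the first plausible and quantifies neither. The spurious odds ratio is about 1.05 to 3.9 under assumed rates, and 1.00 if exposure is unrelated to disease. Because the remedy is cheap and H3 is described as scientifically as important as the primary hypotheses, the wording should be changed.

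**What to change.** In 5.1.4, add that a CMV serology drawn within a defined window after immunoglobulin, or while the child is in an immunoglobulin/placebo trial with unknown allocation, does not make the child CMV positive unless culture confirms it, and does not end CMV serology. State the length of the window. Classify these children from the scheduled urine cultures and the stored urine, and carry the same wording into the footnotes of Tables 9, 10 and 11A. In 7.2, name recorded immunoglobulin exposure as a stratum or covariate for the CMV analysis of H3.

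The cost is a paragraph of wording, a flag derived from treatment data already collected, some CMV serologies that continue instead of stopping, and later classification of a few children.
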